### **6.2.2 Descriptive analyses**

The raw measurements, the change from baseline measurements and the percentage change from baseline measurements of the above secondary efficacy endpoints will be listed by cohort, treatment, participant and visit/time.

Descriptive statistics will be provided for the raw measurements, the change from baseline measurements and the percentage change from baseline measurements of the above secondary efficacy endpoints by treatment and visit/time and will include sample size (n), mean (arithmetic and geometric), SD, CV (arithmetic and geometric), median, minimum, maximum

Commercially Confidential Information

The geometric mean and its

CV will not be reported if the data includes non-positive values. For the change from baseline data summary, the geometric mean and its CV will be based on log-transformed ratio to baseline (i.e., change from baseline in the log scale).

In addition, the proportion of participants with at least 30% relative reduction and 5% absolute reduction in % liver fat (i.e. percentage change from baseline  $\leq -30\%$  and change from baseline  $\leq -5\%$  respectively) will be tabulated separately by treatment.

#### **6.2.2.1 Graphical presentation**

Arithmetic mean (+/- SE) of the raw measurements, the change from baseline measurements and the percentage change from baseline measurements of the above secondary efficacy endpoints will be plotted over time and by treatment (all treatments in the same graph). In addition, geometric mean (+/- 80% CI) of the raw measurements and the ratio to baseline measurements of the above secondary efficacy endpoints will be plotted over time and by treatment (all treatments in the same graph).

Overlaying individual (spaghetti) plots of the raw measurements, the change from baseline measurements and the percentage change from baseline measurements of the above secondary efficacy endpoints will be provided over time and by treatment (one graph per treatment, all participants of each treatment in the same graph).

### **6.2.3 Statistical model, assumptions and hypotheses**

A mixed-effect model for repeated measures (MMRM) analysis will be conducted for log-transformed ratio to baseline in ELF Test and ALT.

Commercially Confidential Information

An

unstructured variance-covariance matrix will be used to account for correlation among multiple measurements from the same participant and variance heterogeneity. If the unstructured covariance causes model convergence issues, then other simpler covariance structures will be considered. Least squares mean, the associated 2-sided 80% confidence interval and the p-value will be obtained for each treatment at each visit and back transformed to the original scale, meaning that the least squares means will be expressed as geometric means after the back-

transformation on the original scale. Contrasts assessing trend over time will be constructed for each treatment using various functional forms as needed. Both cohort-wise and combined cohort analysis will be performed as appropriate.

Log-transformed ratio to baseline in % liver fat, hsCRP, HOMA-IR, HbA1c, fasting glucose, fasting insulin and fasting lipid profile as well as change from baseline in ELF Test, ALT and % liver fat, waist circumference, hip circumference, waist to hip ratio and percentage change from baseline in body weight will also be analyzed. Parameters with more than one post-treatment measurement will be subjected to the same MMRM analysis described above for ELF Test and ALT using untransformed baseline in lieu of log-transformed baseline as a covariate for the untransformed data analysis.

Commercially Confidential Information

Additionally, a multivariate ANCOVA will be done for the three-dimensional endpoint: log-transformed ratio to baseline in ELF Test, ALT and % liver fat at Week 12. The model will include treatment and stratification factor (race and BMI group at baseline) as classification factors and log-transformed baseline as a covariate. An arbitrary 3 by 3 covariance matrix will be assumed for the three-dimensional endpoint.

If there are sufficient data, then a subgroup analysis (ANCOVA) in participants with baseline liver fat  $\geq 10\%$  will be performed to compare % liver fat between treatments.

Commercially Confidential Information

Baseline participant characteristics will be monitored closely and compared across cohorts to assess population drift which may occur because of improved general care and enrollment of either less or more healthy participants over time. The population drift, if present, will be accounted for using a modeling approach as appropriate.

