**Table 4-2 Examples of placebo effect in published studies in NASH and NASH-like patient populations**

Investigational drug	Obeticholic acid (n=23)	Obeticholic acid (n=142)	NGM282 (n=27)	MGL3196 (n=42)	BMS986036 (n=26)
Duration (weeks)	6	12	12	12	16
%Δ ALT from baseline	35.5	-13.4	-2.2	-	-4.5
Relative %Δ liver fat from baseline	-	-	-3.0	-9.6	-
Δ ELF Test from baseline	0.3	-	0	0.1	-
Reference	Mudaliar et al 2013	Neuschwander-Tetri et al 2015	Harrison et al 2018a	Harrison et al 2018b, Abstract GS-009	Sanyal et al 2017

Commercially Confidential Information

Conversely, a review of multiple, recent studies in patients with NASH or a NASH-like (biomarker) phenotype shows that high efficacy, active treatment is associated with relative percent decreases in % liver fat (MRI-PDFF) and ALT of  $\geq 30\%$  ([Sanyal et al 2017](#); [Harrison et al 2018a](#); [Harrison et al 2018b](#)). Similarly, a decrease in ELF Test by  $\geq 0.3$  units or 3% can be considered evidence of a substantive, beneficial reversal in the ongoing liver fibrotic process ([Harrison et al 2018a](#)).

Commercially Confidential Information

Commercially Confidential Information

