## **4.3 Rationale for choice of control drugs (comparator/placebo) or combination drugs**

There is currently no appropriate comparator for use in the NASH/NAFLD patients.

Commercially Confidential Information

---

Commercially Confidential Information

While the primary purpose of NEXSCOT is to detect high efficacy drug combinations, single drug treatment arms may also be studied in those situations where the efficacy of the particular drug on the relevant endpoint biomarkers in the relevant patient population has not been previously measured. In this case, the treatment effects of the single drug treatment arm would be compared to both the combination drug effects and the historical placebo effects.

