## 5 Population

The study population will be comprised of male and female NAFLD patients with a NASH-like biomarker phenotype.

Approximately 25 participants per arm will be enrolled in the study, and around 20 participants per arm are expected to be evaluable. Based on the results of the ongoing data review, the sample size may be increased to an enrollment target up to approximately 50 total for a specific arm; for example, due to higher than anticipated variability of the biomarker data.

Please refer to [Section 17](#) (cohort-specific information) for eligibility criteria specific to each treatment arm.

The investigator must ensure that all participants enrolled into the study meet the following eligibility criteria. No additional criteria should be applied by the investigator, in order for the study population to be representative of all eligible patients.

Participant selection is to be established by checking through all eligibility criteria at both screening and baseline, unless otherwise specified. Please also refer to the [Assessment Schedule](#) for the exact tests to be performed at either visit, but note that certain eligibility criteria may only need to be confirmed to be within the ranges specified at one of the two visits. A relevant record (e.g., checklist) of the eligibility criteria must be stored with the source documentation at the study site.

Deviation from any entry criterion excludes a participant from enrollment/randomization into the study.

Reference ranges for laboratory assessments are located in the standalone laboratory manual.

If any parameters are found to be outside of the range specified in the inclusion or exclusion criteria (where relevant) at screening or baseline, the assessment can be repeated once to rule-out laboratory error or anomaly.

Refer to [Section 8.1](#) (Screening) for information regarding re-screening.

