## 4.1 Cohort-specific information:

### 4.1.1 Cohort 1:

Cohort 1 will evaluate the use of LYS006 alone and tropifexor (LJN452) in combination with LYS006 for the treatment of elevated liver fat, liver inflammation and liver fibrosis in NAFLD participants who manifest a NASH-like biomarker phenotype. The drug combination of LYS006 and tropifexor (LJN452) may provide clinical benefit beyond that of either drug alone, considering different, complementary mechanisms of action of these drugs.

Approximately 50 participants will be randomized in a 1:1 ratio to one of the following treatment arms:

- Treatment arm 1: LYS006 Commercially Confidential Information
- Treatment arm 2: Tropifexor (LJN452) Commercially Confidential Information + LYS006 Commercially Confidential Information

The treatments used in cohort 1 (i.e. LYS006 and Tropifexor) do not have extended half-lives, so the EOS1 visit will serve as the end-of-study visit for participants randomized to any of the two treatment arms of cohort 1 (i.e. for all cohort 1 participants).

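### The per-arm p-values for ELF and ALT have no stated null and no placebo arm behind them, so they cannot separate drug effect from placebo drift

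*SAP*

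**What the plan says.** SAP 6.2.3 says of the mixed model that the "analysis will be conducted for log-transformed ratio to baseline in ELF Test and ALT". It continues: "Least squares mean, the associated 2-sided 80% confidence interval and the p-value will be obtained for each treatment at each visit", with results back-transformed to geometric means. Protocol 12.5.1 has the same sentence, and so does the data-analysis entry of the Protocol summary, where the model terms are visible. None of the three gives a null value or a significance level.

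For % liver fat the link is looser. The Protocol summary says it is handled in a similar way. Protocol 12.5.1 assigns it an ANCOVA without saying what inference is reported.

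The one between-treatment efficacy comparison stated in the visible text is for % liver fat in participants with baseline liver fat of at least 10%, if data suffice. The Week 12 multivariate ANCOVA has treatment as a factor but names no contrast. By comparison, SAP 5.3 spells out between-treatment differences with 90% intervals for PK.

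On design, SAP 4.1.1 says "Approximately 50 participants will be randomized in a 1:1 ratio to one of the following treatment arms": LYS006 alone, or LYS006 with tropifexor. Neither is a placebo. Protocol 5 says "Approximately 25 participants per arm will be enrolled in the study, and around 20 participants per arm are expected to be evaluable". Protocol 4.3 says that the effects of a single-drug arm "would be compared to both the combination drug effects and the historical placebo effects".

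Protocol Table 4-2 lists published placebo changes. The ALT row reads "Δ ALT from baseline 35.5 -13.4 -2.2 - -4.5". The row "Relative %Δ liver fat from baseline" gives -3.0 and -9.6. The ELF row gives 0.3, 0 and 0.1.

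**The concern.** A p-value attached to one arm's mean log ratio to baseline is, by default, a test that the ratio equals 1. That would indicate drug effect only if untreated participants stayed at baseline. The protocol's own table shows that they do not. Placebo liver fat fell in both studies that report it. Placebo ALT fell in three of four and rose in the fourth. A small p-value can therefore come from drift alone, and a rise under placebo could make an inactive or modestly active drug look harmful.

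Protocol 1.2 says that the data are meant to support selection of high-efficacy regimens. Protocol 17.1.1.3 wants the single agent compared with the combination, to judge whether effects are additive, synergistic or antagonistic. Neither question is answered by a change-from-baseline test within one arm, while a randomised contrast that bears on the second is available.

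**Working it through.** The visible text gives no power, significance level, effect size or SD, so there is no stated figure to reproduce. The check asks how often an inactive arm's interval would exclude no change.

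**Inputs**
- n = 20 evaluable per arm (Protocol 5).
- Two-sided 20% level, from "the associated 2-sided 80% confidence interval" (SAP 6.2.3). The 5% level is run as well, as an assumption.
- Placebo changes from Protocol Table 4-2.
- SD of the log ratio to baseline: not in the documents. Assumed 0.25 to 0.45.

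**Formula.** One-sample t on the log ratio with 19 df. The non-centrality is ln(1 + change) / (SD/√20). The critical value at the 20% level is 1.328. Covariates and repeated visits are ignored, and Table 4-2 percentages are treated as geometric mean changes.

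**Worked line.** ALT -13.4%: ln(0.866) = -0.1439. With SD 0.35, SE = 0.35/√20 = 0.0783 and the non-centrality is -0.1439/0.0783 = -1.84. The probability of exclusion is 0.70.

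**Percentage of trials in which the 80% interval excludes no change, with no drug effect**

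| Placebo drift | SD 0.25 | SD 0.35 | SD 0.45 |
|---|---|---|---|
| none | 20 | 20 | 20 |
| ALT -13.4% | 89 | 70 | 55 |
| ALT -4.5% | 34 | 27 | 24 |
| ALT -2.2% | 23 | 22 | 21 |
| ALT +35.5% (as a rise) | 100 | 99 | 95 |
| Liver fat -9.6% | 69 | 50 | 39 |
| Liver fat -3.0% | 26 | 23 | 22 |

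At the 5% level the figures are 27-69% for ALT -13.4% and 16-40% for liver fat -9.6%.

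**Weighted by study size.**
- Liver fat: (27 × -3.0 + 42 × -9.6)/69 = -7.0%.
- ALT, all four studies: (23 × 35.5 + 142 × -13.4 + 27 × -2.2 + 26 × -4.5)/218 = -5.8%.

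Counting only falls (nominal 10%) and widening the assumed SD to 0.2-0.5, an inactive arm shows a significant fall in 26-62% of trials at liver fat -7.0% and 22-51% at ALT -5.8%.

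**ELF.** Placebo changes are zero or upward, so a test against no change does not tilt towards apparent benefit.

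**Against the protocol's own benchmark.** Protocol 4.1.3 links high efficacy to falls of at least 30% in ALT and liver fat. An inactive arm's geometric mean reaches that with probability at most 0.03 (ALT -13.4%, SD 0.5), and at most 0.011 for liver fat.

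**Would one fixed historical reference cure it?** Not reliably. If the true liver-fat drift is -9.6% and the reference is set at -3.0%, a significant fall appears in 60 / 40 / 31 / 25% of trials at SD 0.2 / 0.3 / 0.4 / 0.5, against a nominal 10%.

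**The case against.** A reader might infer that the plan would often pass an inactive drug as effective and so favour advancing it. The documents do not support that, for these reasons:

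- No visible rule turns this p-value into a decision. The visible yardsticks are the 30% benchmark, the tabulated proportions with 30% relative and 5% absolute liver-fat reduction, and the liver-fat subgroup comparison. An inactive arm would rarely reach the 30% benchmark on its mean.
- High rates of apparent benefit come from the largest fall for each marker and from an assumed SD. At the smaller falls the excess over nominal is modest, one ALT placebo arm rose by 35.5%, and ELF did not fall.
- The null of no change is an inference. Text is redacted in SAP 6.2.3, in Protocol 12.5.1, in Protocol 4.3 and after Table 4-2. A reference value or a placebo comparison could sit there, so its absence cannot be asserted.
- The sentence on historical placebo in Protocol 4.3 is limited to single-drug arms. It also shows that the sponsor intends such a comparison.
- The quoted inference sentence covers ELF and ALT. Liver fat is reached only through the Protocol summary.
- The endpoints are secondary in a study declared non-confirmatory.

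All of this stands, and it limits the point. It does not give the planned p-value a usable meaning. With placebo ALT ranging from -13.4% to +35.5%, a test against no change cannot isolate drug effect in either direction. The benchmark and responder table are separate descriptive yardsticks and do not repair it.

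**Conclusion.** The point holds in a limited form and is worth acting on. In the visible text, ELF and ALT inference is per arm and against an unstated null that reads as no change, with no placebo arm. That p-value describes change from baseline and should not be read as efficacy.

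The size depends on which placebo history applies and on the assumed SD of 0.25-0.45 with n = 20. Exclusion of no change by an inactive arm ranges from close to the nominal 20% at the smallest falls to 89% at the largest, and is near certain, as a rise, at ALT +35.5%. If the Table 4-2 percentages are arithmetic means of individual changes, the corresponding geometric ratios are lower than those used here. That would enlarge the apparent falls and shrink the apparent rise.

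Not established: that the placebo comparison is missing from the full plan, that the p-value drives selection, or that ELF is affected in the direction of benefit.

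**What to change.** 1. From the MMRM and ANCOVA already planned, report the Arm 2/Arm 1 ratio with its 80% interval for ALT, ELF and % liver fat. With 20 per arm the log half-width is 1.304 × SD × √(2/20), which is 0.103 to 0.186 for SD 0.25-0.45. The interval is therefore the ratio multiplied and divided by 1.11 to 1.20. This contrast isolates the added effect of tropifexor. It says nothing about LYS006 against placebo.
2. State the null of the within-arm p-value. Then drop the p-value, or label it as a test of change from baseline that is not evidence of efficacy.
3. If the redacted text does not already do so, set each arm's LS mean ratio and interval beside the range of Table 4-2 placebo values, with their uncertainty. Do not test against one fixed worst-case value: it would not guarantee the error rate, and it would penalise an active drug if true drift is smaller.

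The cost is a few sentences in the SAP and one contrast per model, with no new data. The downside is that fewer within-arm results will look significant.

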#### **6.2.3.1 Handling of missing data**

Missing data will not be imputed for the univariate MMRM analysis. Assuming data is missing at random, a participant with missing value at a visit will still contribute to the estimation of the treatment effect at that particular visit as the likelihood-based MMRM borrows information from non-missing values of this participant and other participants.

For the Week 12 multivariate ANCOVA, an additional analysis with the last post-treatment observation carried forward for missing ELF Test and ALT values may be performed.

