## 6 Statistical methods for Efficacy/Pharmacodynamic (PD) parameters

All participants within the efficacy/PD analysis set will be included in the efficacy/PD data analysis.

Data will be excluded from the efficacy/PD analyses in the following cases:

- For participants with protocol deviations affecting the efficacy/PD analyses, the data will be excluded as described in [Table 4-1](#) above.
- For participants that discontinued treatment early, the following *programming rule* will be applied: *Any efficacy assessments that occurred on or after the treatment discontinuation study day, will be excluded from all efficacy/PD data analyses. An exception to this is the Day 85 visit or EOS visit imaging data (MRI and MRE assessments), that will be excluded only if they occurred prior to study day 56 (i.e., imaging assessments that occurred on or after study day 56, will not be excluded from the imaging analyses).*
- Participants with <80% treatment compliance

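### The only visible missing-data method for the Week 12 joint ELF, ALT and liver-fat analysis is an optional last-observation-carried-forward run, which pulls the estimate toward Day 57 or earlier; imputing from earlier visits is better and cheap

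*SAP*

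**What the plan says.** SAP 6.2.3 states that "a multivariate ANCOVA will be done for the three-dimensional endpoint", formed by the log-ratios to baseline of ELF Test, ALT and % liver fat at Week 12. On covariance it adds "An arbitrary 3 by 3 covariance matrix will be assumed for the three-dimensional endpoint". The visible text does not say whether a participant with one or two components missing contributes to this model or is dropped.

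SAP 6.2.3.1 deals with missing data in two parts:

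- For the repeated-measures models of single markers: "Missing data will not be imputed for the univariate MMRM analysis". The reason given is that, under missing at random, "the likelihood-based MMRM borrows information from non-missing values of this participant and other participants".
- For the Week 12 joint model: "an additional analysis with the last post-treatment observation carried forward for missing ELF Test and ALT values may be performed". Protocol 12.5.1 repeats this. I read post-treatment here as after the first dose, which is how SAP 6.2.3 uses the word elsewhere.

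SAP section 6 sets the rule for early discontinuation: "Any efficacy assessments that occurred on or after the treatment discontinuation study day, will be excluded from all efficacy/PD data analyses". Imaging is the exception: "imaging assessments that occurred on or after study day 56, will not be excluded from the imaging analyses".

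Three other places matter:

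- Protocol Table 8-1, footnote 5, makes Day 71 a telephone contact.
- Protocol 8.3.3 requires participants who stop on or after Week 8 to be scanned as near to the last dose as possible. SAP Table 4-1 (code OTH12) excludes imaging not done within 7 days of discontinuation.
- Protocol 4.2 regards twelve weeks as the shortest treatment period in which measurable change in inflammation, fat and fibrosis can be expected.

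**The concern.** Carrying a value forward assumes that nothing changes between the last sample and Week 12. The sponsor's own rationale in Protocol 4.2 argues against that. The exclusion rules also create the cases to be filled: someone who stops between about Day 56 and Day 85 can have a usable scan but no Week 12 ELF or ALT. The carried run would then enter an older blood value in a vector labelled Week 12.

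At stake is the size of the Week 12 ELF and ALT effects in the joint analysis. The plan already uses a likelihood method under missing at random for the same two markers, so a better option is at hand. Carrying forward also does nothing for a participant whose missing component is liver fat, because MRI is done only at baseline and end of treatment.

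**Working it through.** The plan gives no figure to reproduce here: no SD, missingness rate or power for the joint analysis is visible.

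**1. Age of the carried value.** With Day 71 by telephone, the last scheduled blood sample before Day 85 is Day 57. The gap is 85 - 57 = 28 days, one third of the 84-day treatment period. If treatment stops on or before Day 57, the Day 57 sample is itself excluded and the carried value is older. An unscheduled sample could shorten the gap.

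**2. Gap between bloods and scan.** Take Day 57 bloods and a scan no more than 7 days after stopping. A stop on Day 60 gives at most 67 - 57 = 10 days. A stop on Day 84 gives 27 to 34 days. The mismatch therefore runs from days to roughly four or five weeks.

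**3. Size, by formula.** Let m be the share carried forward in the arm with the effect, and f the effect at the carried visit divided by the Week 12 effect. Assume a flat comparator and missingness unrelated to response. Then

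share of the Week 12 log-effect kept = 1 - m(1 - f).

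For a true 30% ALT fall, the benchmark in Protocol 4.1.3, the apparent fall is 1 - 0.7^(share kept). For example, m = 0.20 and f = 0.5 give 1 - 0.20 × 0.5 = 0.90, and 1 - 0.7^0.90 = 27.5%.

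| m | f = 0.5 | f = 0.7 | f = 0.9 | f = 1.0 | f = 1.2 |
|---|---|---|---|---|---|
| 10% | 28.7% | 29.2% | 29.7% | 30.0% | 30.5% |
| 20% | 27.5% | 28.5% | 29.5% | 30.0% | 31.0% |
| 30% | 26.2% | 27.7% | 29.2% | 30.0% | 31.5% |

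For ELF, a true change of -0.30 at m = 20% would read -0.270 (f = 0.5) to -0.312 (f = 1.2). The values of m and f are assumptions. The one anchor in the documents is Protocol section 5: 25 enrolled and about 20 evaluable per arm, an implied 20% non-evaluable.

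**4. Size, by simulation.** The assumptions were 25 per arm, log-SD 0.35, correlation 0.6 between visits, a true ALT contrast of -30%, and 10-30% missing in one arm. Carrying forward gave -25.3% to -31.1%, depending on the effect's time course. An estimate using the earlier visit stayed at about -30%. A second set used correlation 0.7, 20% missing and a true log-ratio of -0.357:

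| Scenario | Carried forward | Likelihood |
|---|---|---|
| f = 0.5, completely at random | -0.324 | -0.359 |
| f = 0.5, at random | -0.329 | -0.356 |
| f = 1.2, at random | -0.374 | -0.361 |

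In that set, complete cases under missing at random averaged -0.340 to -0.345. Leaving the main joint model's rule unstated is therefore not harmless either. The direction of that bias depends on the missingness mechanism.

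**5. Against the precision available.** The SE is 0.35 × √(2/25) = 0.099, so an 80% interval has a half-width of about 1.28 × 0.099 = 0.13. The worst attenuation is ln(0.747) - ln(0.700) = -0.292 + 0.357 = 0.065, about half of that. The worst inflation in the simulation is ln(0.689) - ln(0.700) = -0.373 + 0.357 = -0.016.

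**The case against.** The strongest reply is that this is an optional extra. The text makes it additional and says only that it may be done, so deleting it changes no planned estimate. Week 12 ELF and ALT effects come from the repeated-measures models without imputation. The study is non-confirmatory and efficacy is secondary. All of that stands and sets the weight.

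A reader might infer three stronger points that the documents do not support:

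- *That the plan switches to carrying forward for the joint endpoint.* It does not: the multivariate ANCOVA is planned without it.
- *That the joint endpoint is the plan's summary of efficacy.* The secondary endpoints are the separate markers. The joint model is introduced as an addition, and no visible decision rule uses it.
- *That carried-forward intervals are too narrow.* The carried estimate does vary slightly less than the likelihood one (SD about 0.10 against 0.105 to 0.108 at 20% missing), but that is its true sampling variability. In a check with 25 per arm, its model-based SE was 0.099-0.104 against an empirical SD of 0.099-0.105. Nominal 80% intervals covered 76-81%. The lowest value came from bias at 30% missing, not from understated error.

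The scan-timing rules also limit the mismatch within a vector, as step 2 shows. Nor is carrying forward always conservative: it inflates an effect that peaked early. Finally, parts of SAP 6.2.3 and SAP section 11 are redacted, so the claim that this is the only method applies to the visible text. SAP 6.2.3.1 itself shows no redaction.

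**Conclusion.** The point holds as a minor one, a cheap improvement. In the visible text, an optional carried-forward run is the only missing-data method for the Week 12 joint analysis. It substitutes a value normally at least 28 days old, in a plan that already has a better method for the same markers. The shift is roughly 0 to 5 percentage points on a 30% ALT reduction, toward whatever the effect was at the earlier visit. That range rests on assumed missingness of 10-30% in one arm, a log-SD of 0.35, visit correlation of 0.6 and an assumed time course. It was worked for ALT alone, not the full three-part vector. If little is missing or the effect is already stable by Day 57, the shift is close to nil: at 5% missing the formula gives 29.4% to 30.2%.

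**What to change.** Replace the carried-forward sentence in SAP 6.2.3.1 and Protocol 12.5.1 with wording to this effect:

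*For the Week 12 multivariate ANCOVA, missing ELF Test and ALT values will be multiply imputed under missing at random from treatment, stratum, baseline, earlier on-treatment ELF Test and ALT values, and liver fat where available. The joint model will be fitted by likelihood, so that participants with any observed component contribute.*

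This makes the same missing-at-random assumption as the single-marker models, settles how incomplete vectors are handled, and covers missing liver fat. If the carried-forward run is kept, label it descriptive.

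A single unstructured covariance over all visits is not needed and would be impractical. Five ALT visits, two ELF visits (counts assumed, as Table 8-1 is broken in the text) and one scan make 8 variables, with 8 × 9 / 2 = 36 covariance parameters for about 50 participants.

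The cost is one sentence in each document and modest programming. No visit, sample or participant is added.
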